- 2. To study safety, tolerability and quality of life in the trial period of liraglutide vs placebo application
- 3. To collect first data about the efficacy of a liraglutide therapy in patients with an ileo-anal pouch anastomosis (IPAA) and abnormal high bowel frequency in the absence of inflammation for planning a larger phase 3 study in this orphan status patient population

STUDY DESIGN

Randomized, double-blind, 2-period, placebo- controlled, crossover proof of concept study. Ten patients with increased bowel frequency is defined as > 8 bowel daily/week without significant pouchitis* will be randomized to either liraglutide or placebo treatment for 6 weeks (Period 1). Subjects will be randomized 1:1 to 1 of 2 treatment sequences, liraglutide-placebo or placebo-liraglutide, and receive either liraglutide or volume-matched placebo. After a washout period of at least 5 days (the half-life of liraglutide is 11-12 hours, thus the minimal washout period of 5 days is equal to 10 half-life's) patients will be crossed over to the other treatment arm (Period 2). Since high bowel frequency can result in significant malaise and dehydration, patients not responding to the respective therapies in period 1 may be crossed over after 4 weeks of therapy or in period 2 can be terminated early at week 4. The rationale behind the early termination is based on 2 open label cohorts reporting the efficacy of liraglutide or exenatide in patients with high output ileostomies (the patient group the most comparable to the pouch patient population). GLP-1 receptor agonist therapy even at the lowest dose showed an almost immediate effect reducing the ostomy output after 1-3 days in most patients.^{26, 27} Thus, patients not responding to a 4-week therapy with a GLP-1receptor agonist are highly unlikely to respond if the therapy would be continued.

[figure not shown]

Figure 3: Study design

Randomization: Subjects will be randomized 1:1 to 1 of 2 treatment sequences, liraglutide—placebo or placebo—liraglutide, and receive either liraglutide or volume-matched placebo.

STUDY DRUG, SUPPLY OF STUDY DRUG AND RECRUITMENT PLAN

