 - o Specific laboratory test supporting a diagnosis of gallstone disease

- Imaging performed and consistency with gallstone disease
- New onset of Pancreatitis confirmed if a minimum 2 of 3 criteria ae met:
 - Severe acute abdominal pain
 - Blood amylase and/or lipase >3x upper limit of normal (ULN)
 - Characteristic findings on relevant imaging (e.g., computerized axial tomography/magnetic resonance imaging/ultrasound)
- Any medical condition or clinically significant abnormal finding(s) (physical, laboratory, vital sign) that may jeopardize the subject's safety if study drug is continued, in the investigator's and/or sponsor's opinion; this may include the development of persistent events such as:
 - o ALT or AST > 3x ULN and either total bilirubin > 2x ULN or INR > 1.5
 - ALT or AST > 3x ULN with the appearance of fatigue, nausea, vomiting, right upperquadrant pain or tenderness, fever, rash, and/or eosinophilia (> 5%)
 - Creatinine elevation > 2x above upper limit of normal
- Recurrent hypoglycemia defined as a blood glucose of ≤ 3.9 mmol/L (70 mg/dL)
- other reasons (noting reason)

Reasons leading to the **stop of study drug but follow-up according protocol** can include the following (primary reason must be determined):

- lack of efficacy of the study medication, e.g.
 - need for a prohibited concomitant medication (e.g. need for steroids)
- lack of patient's cooperation, e.g.
 - patient's request
 - lack of compliance (fails to attend the follow-up visits as agreed)
 - existing pregnancy or intended pregnancy* (females), lactation (females)

In all patients who finish the study prematurely, a withdrawal examination should be carried out within 2 weeks after the last application of the study medication. The withdrawal examination must be conducted as a final examination and documented in the CRF.

REPLACEMENT OF WITHDRAWN PATIENTS

Replacement lists will not be provided since it is not planned to replace subjects if they withdraw or become ineligible after the first dose of study drug has been given.

CRITERIA FOR THE TERMINATION OF THE WHOLE STUDY

If safety concerns arise, the PI can terminate or interrupt the study by agreement with Novo-Nordisk. If new information on the risk-to-benefit ratio of the drug or on the treatment methods

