used in the study is obtained in the meantime, the PI reserves the right to interrupt or terminate the project by agreement with Novo-Nordisk. Premature termination is also possible if patient recruitment is insufficient and cannot be expedited by appropriate measures.

LIABILITY AND SUBJECT INSURANCE

The PI (sponsor-investigator) and his/her institution will provide adequate medical care to the study subject for any study-related adverse events, including clinically significant laboratory values related to the study. Sponsor-investigator should state that this medical care for study subjects will be provided regardless of their insurance status.

The PI (sponsor-investigator) will be responsible for the conduct of the study. The PI (sponsor-investigator) agrees to defend, indemnify, and hold harmless Novo Nordisk, any of its parent companies, affiliates, or subsidiaries, and their respective officers, directors, employees, agents, representatives, distributors, salespersons, customers, licensees, and end-users from and against any claim, suit, demand, loss, damage, expense or liability imposed by any third party arising from or related to: (a) any breach of PI's (sponsor-investigator's) obligations or representations; or (b) PI (sponsor-investigator's) negligent or grossly negligent use or willful misuse of the study drug, the results, or services derived therefrom. This indemnification shall not apply in the event and to the extent that a court of competent jurisdiction or a duly appointed arbiter determines that such losses or liability arose as a result of Novo Nordisk's gross negligence, intentional misconduct, or material breach of its responsibilities.

RANDOMIZATION, DATA MANAGEMENT AND DATA MONITORING

The randomization sequence of the patients and the processing and analysis of the data will be carried out by the Biostatistics core of the Center for Gastrointestinal Biology and Disease at UNC Chapel Hill. The randomization sequence will be established by the CGIBD Biostatistics core and communicated with the investigational drug services of UNC.

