The primary outcome is the reduction of the mean 7-day bowel frequency of 30% compared to baseline (baseline is defined as the mean 7-day bowel frequency in a 7-day period during the screening period before week 0). A crossover trial will be performed. Subjects with a history of averaging > 8 bowel movements per day over a 7-day span will be entered into the study and the

order in which they receive treatments (liraglutide or placebo) will be randomized. At the end of each week, the average number of bowel movements the subject had during that week will be computed. A repeated measure mixed model will be fit to the data with treatment (liraglutide or placebo), period and treatment sequence as fixed effects and the repeated measures within subject as a random effect. After the model is run, any non-significant effects for period or treatment sequence will be removed from the model. The treatment effect will remain in the model and is the outcome of interest. P-value less than 0.05 will be considered statistically significant. In a sensitivity analysis the same model will be run without removing any effects. P-value less than 0.05 will be considered statistically significant.

Secondary analyses

Continuous secondary outcomes (stool frequency, clinical PDAI) will be summarized using descriptive statistics (mean, median, standard deviation, minimum, and maximum) of the values at each assessment and the change from baseline to each assessment. A repeated measure mixed model will be fit to the data with treatment (liraglutide or placebo), period and treatment sequence as fixed effects and the repeated measures within subject as a random effect. After the model is run, any non-significant effects for period or treatment sequence will be removed from the model. The treatment effect will remain in the model and is the outcome of interest. P-value less than 0.05 will be considered statistically significant.

Safety analyses

The safety analyses will comprise all included patients, who got at least one dose of the investigational product.

- Number of study patients, who discontinued therapy
- Adverse events grouped by body system
- Changes in laboratory values

Exploratory analyses

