We will perform exploratory analyses using descriptive statistics (mean, median, standard deviation, minimum, and maximum) and bivariate analyses of the values at each assessment and the change from baseline to each assessment. In the evaluation of the PROMIS measure for incontinence, PROMIS measures utilize a T-score metric where a score of 50 is the mean of a relevant reference population and 10 is the standard deviation. Additionally, a clinically minimally important difference is reflected by a change of 2.

Missing data

Due to short and intensive period of follow-up for the primary outcome, we do not anticipate significant missing data.

SAMPLE SIZE CALCULATION

The analysis will be based on the within-subject difference between two one-week averages of the number of bowel movements per day (BMPD). A one-sample t-test will be used to test the

null hypothesis that the mean difference is zero. With a sample size of 10 subjects and Type-I 0.05 (2-sided), the power is 0.80 against a difference of 1 standard deviation (SD) of the difference (not SD of the individual outcomes). The first average within each patient, by design, will be greater than 8 BMPD, and the range is most likely to be 8-11. The standard deviation (SD) of such an outcome can't (mathematically) exceed 1.5, and this will be used in the sample size calculations as the SD of each weekly average (control and treatment). Additionally, the SD of the difference depends on the correlation between the two weekly averages. Taking that into account, the power is 0.80 against a difference of 2.1 BMPD if the correlation is 0, 1.8 BMPD if the correlation is 0.25, 1.5 BMPD if the correlation is 0.50, 1.1 BMPD if the correlation is 0.75. Assuming a baseline average of 10 BMPD, the design has good power against relative changes of 21% or higher if the within-subject correlation is zero. The power increases with increasing positive correlation and, naturally, is higher against larger effects. If patients drop out during the study the power will decrease, however patents will be carefully selected and thus dropouts are unlikely to occur.

FUTURE PERSPECTIVE

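### The crossover models drop period when it is not significant; with 10 patients that test is weak, and dropping a real period effect biases the treatment effect if the sequences are unequal

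*Combined protocol and SAP*

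**What the plan says.** Under Data Analysis, the Primary analyses paragraph fits a repeated-measures mixed model to weekly averages ("At the end of each week, the average number of bowel movements the subject had during that week will be computed"), with treatment, period and sequence as fixed effects. It then states: "After the model is run, any non-significant effects for period or treatment sequence will be removed from the model". Treatment stays in and is judged at 0.05. The unpruned model follows as a check: "In a sensitivity analysis the same model will be run without removing any effects". The Secondary analyses paragraph repeats the model and the removal rule but not the check.

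On balance between sequences, Study Design says "Subjects will be randomized 1:1 to 1 of 2 treatment sequences". The Randomization section says who makes the list ("The randomization sequence will be established by the CGIBD Biostatistics core and communicated with the investigational drug services of UNC") but describes no blocking. Lost patients are not made up: "Replacement lists will not be provided since it is not planned to replace subjects if they withdraw".

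**The concern.** The rule picks the model from the trial data and then reads the treatment p-value as if no choice had been made. It treats a non-significant period test as showing that period can be ignored, and 10 patients cannot support that.

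Period is the term that matters. Dropping sequence alone barely changes a within-patient treatment comparison. Dropping a real period effect does no harm to the estimate if the sequences are equal and the data complete. If they are unequal, part of the period effect is counted as treatment effect. At stake are the headline p-value and effect estimate of a study meant to inform a larger trial, and all the secondary results, which have no unpruned check.

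**Working it through.** **Inputs from the plan** (Sample Size Calculation): 10 patients; two-sided 0.05; one-sample t-test on within-patient differences; SD of a weekly average 1.5; stated power 0.80 at 1 SD of the difference.

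**Assumptions, not in the plan:** a period effect of 0, 0.5 or 1.0 bowel movements per day (BMPD); sequence splits from 5/5 to 8/2; no treatment effect when type I error is computed.

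**The plan's own figure.** One-sample t, noncentrality √10 = 3.16, 9 df: power 0.803, so the stated 0.80 is reproduced. With SD of the difference = 1.5 × √(2(1 − ρ)), the differences detectable with 80% power are 2.11, 1.83, 1.49 and 1.06 BMPD at ρ = 0, 0.25, 0.50 and 0.75, which matches the plan. That calculation has no period term.

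**Bias if period is left out.** Write π for the period effect, and n₁ and n₂ for the numbers in the two sequences. The liraglutide-minus-placebo difference has mean τ − π in one sequence and τ + π in the other. The simple average is therefore off by π × (n₁ − n₂)/(n₁ + n₂) in size: 0 at 5/5, 0.20π at 6/4, 0.40π at 7/3, 0.60π at 8/2.

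**Strength of the period test.** The standard error of the period effect is (SD of difference / 2) × √(1/n₁ + 1/n₂). At 5/5 with SD 1.5 this is 0.75 × √0.4 = 0.474. A period effect of 1.0 BMPD then has noncentrality 1.0/0.474 = 2.11 on 8 df and is significant 46% of the time.

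**Setting (a): one value per period, SD of difference 1.5 (ρ = 0.50), π = 1.0 BMPD, 200,000 simulated trials per split.** The rule uses the period-adjusted t-test (8 df) if period has p < 0.05, and otherwise the one-sample t-test (9 df).

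| Split | Period kept | Bias under the rule (BMPD) | Type I error, rule |
|---|---|---|---|
| 5/5 | 46% | 0 | 0.048 |
| 6/4 | 44% | 0.08 | 0.053 |
| 7/3 | 40% | 0.17 | 0.075 |
| 8/2 | 32% | 0.30 | 0.130 |

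**Setting (b): four weekly averages per period, closer to the planned model.** Random patient intercept, weekly SD 1.5, ρ = 0.5, independent weekly residuals, 100,000 trials per split. An effect of 1.0 BMPD is now kept in 97–99% of trials from 5/5 to 7/3, and at 7/3 the bias is under 0.01 with type I error 0.057. A smaller effect of 0.5 BMPD is still often dropped:

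| Split | Period kept | Bias under the rule (BMPD) | Type I error, rule |
|---|---|---|---|
| 5/5 | 55% | 0 | 0.050 |
| 6/4 | 53% | 0.03 | 0.057 |
| 7/3 | 48% | 0.06 | 0.091 |
| 8/2 | 38% | 0.12 | 0.164 |

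With six weeks per period, the 0.5 BMPD effect at 7/3 gives bias 0.04 and type I error 0.089. With no period effect, the rule's type I error from 5/5 to 7/3 is 0.054–0.058 in (a) and 0.050–0.054 in (b). The model that keeps period has zero bias and type I error 0.049–0.051 throughout both settings.

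**How likely is an unequal split?** If allocation is unrestricted (an assumption), exactly 5/5 has probability 0.25, 6/4 either way 0.41, 7/3 either way 0.23, and anything more extreme 0.11.

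**Early crossover.** The plan lets week-4 non-responders cross early. At 5/5, if only placebo-first patients did so and the missing weeks were not filled in, leaving out period would bias treatment by 0.06π (three of five crossing) to 0.11π (all five).

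**The case against.** The strongest reply is that the unpruned model is already planned for the primary outcome at the same 0.05, so the change only swaps two analyses, and that harm needs both a real period effect and clearly unequal sequences. The plan states no period effect. Silence on blocking does not prove simple randomisation. One withdrawal from 5/5 leaves 5/4, which is nearly harmless: bias at most 0.05 BMPD and type I error 0.049–0.055 across both settings. Withdrawn patients may even stay in the analysed split through the modified intention-to-treat set and last observation carried forward. Averaged over simple randomisation, type I error is 0.056–0.068 in (a) and 0.053–0.078 in (b) for period effects of 0 to 1.0 BMPD. The biases are also small beside the 1.5 BMPD the plan is powered for at ρ = 0.50.

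All of this is fair and limits the size of the problem. It does not rescue the rule: if the two p-values fall on either side of 0.05, the declared result is the one with the weaker guarantee, and the secondary outcomes have no second analysis.

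A further objection is that keeping period does not by itself protect the p-value. With an assumed patient-by-period SD of 0.5 or 0.75 BMPD, the unpruned model of setting (b) has type I error of about 0.13 or 0.21 at 5/5. That is correct, but it affects the pruned and unpruned models alike. It is a separate question about the covariance structure.

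**Conclusion.** The concern holds. The removal rule governs the main analysis of both outcome sets, and a small or moderate period effect would often be missed. How often depends on the data used: 1.0 BMPD is missed in about half of trials with one value per period but almost never with four weekly averages, where 0.5 BMPD is missed in about half.

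The harm is nil with complete, equal sequences, small at 6/4 or 5/4, and material from 7/3 onward, where type I error is 0.075–0.091 in the affected scenarios, rising to 0.130–0.164 at 8/2. These sizes rest on assumed period effects, correlations and splits. The existing sensitivity analysis softens the problem for the primary outcome only. This is a change the plan should make, not a flaw that invalidates the trial.

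**What to change.** In both the Primary and Secondary analyses paragraphs, replace the removal sentence with one saying that treatment, period and sequence stay in the model whatever their p-values, and that the treatment test from this model is the reported result. Keep the reduced model at most as a sensitivity analysis. If the randomisation list has not been issued, block it so that five patients enter each sequence.

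The edit is one sentence in each of two paragraphs, and the model is already specified. The price is some power. At 1 SD, with one value per period, the full model has power 0.79 at 5/5, 0.77 at 6/4, 0.72 at 7/3 and 0.60 at 8/2, against the stated 0.80. After one loss from 5/5 it is 0.73, against 0.75 for the one-sample t-test with nine patients. If there is truly no period effect, the removal rule has slightly more power at 5/5 (0.81 against 0.79). Blocking holds the cost against the stated 0.80 to about one point.

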If at visit week 4 the bowel frequency of the patient did not respond to treatment (at least a 15% decrease compared to baseline the patient can proceed to early crossover. The patient will be given study drug (either the placebo or the liraglutide group) in medication packs with his unique study ID medication packs, which will be containing treatment until week 12 and be instructed to bring back the study medication from study period 1 at the final visit of period 2 (week 12). He will be instructed to start injections on day 6 after 5 days of washout. The day he starts will be defined as week 6 period 2.

Visit week 6 period 1 (site visit): If the patient did not qualify for early crossover, he will come to visit week 6 period 1 the coordinator will review the adverse events, which occurred since the previous visit. A physical exam and blood tests will be performed and the mPDAI will be calculated. The concomitant medications will be assessed. If subject is a woman of child-bearing potential, a reliably and highly effective contraceptive method will be confirmed. A stool sample will be collected from the patient either at visit or days -2 - +2 around the study visit as mail in. Female patients will provide urine samples for pregnancy test at week 6 period 1. The patient will be given either the placebo or the liraglutide group with his unique study ID for period 2 and will be instructed to start injections on day 6 after 5 days of washout. The day he starts will be defined as week 6 period 2. The patients will be also be instructed to bring back the study medication from study period 1 at the final visit of period 2 (week 12). There will also be a review of glucose diary and hypoglycemic protocol and reporting form.

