- Adverse events (review adverse events diary)
- Review of glucose diary and hypoglycemic protocol and reporting form
- Concomitant medication
- Calculation of clinical mPDAI
- Remind of stool sample collection at Period 2 week 7 for Period 2 week 8 and at Period 2 week 8 for Period 2 week 10
 - Confirm reliable and highly effective contraceptive method if subject is a woman of child-bearing potential

VISIT PERIOD 2 WEEK 10: (SITE VISIT; =/- 3 DAYS)

- Head (including ENT and eyes)

Examinations

- Vital signs: blood pressure (mm Hg), heart rate (min-1), weight (kg), temperature

- Gastrointestinal tract, liver, spleen

- Physical examination:
- Lymphatic system- Endocrine system- Nervous system
- Lungs and respiratory tract
 Peripheral vascular system
 Skin and connective tissue
- Cardiovascular system Other each: actual status: Present finding / normal condition / not examined

Blood sampling and measurement of laboratory parameters

- Labs
- Urine pregnancy test (female)
- Check if stool sample was received

Formal aspects:

- Adverse events (review adverse events diary)
- Confirm reliable and highly effective contraceptive method if subject is a woman of child-bearing potential
- Review of glucose diary and hypoglycemic protocol and reporting form
- Concomitant medication
- Calculation of clinical mPDAI and assess if patient is responder or not (early termination in case of non-responder). If non-responder, patient should stop medication and will be considered early termination
- If patient continues reminder stool week 12.
- Early termination: Remind patient to come to final visit at Period 2 week 12 and bring all study medication of (if not done already from Period 1 and complete from Period 2). For this patient group at visit Period 2 week 12 only adverse events (review adverse events diary) and concomitant medication will be assessed. An alternative approach is a phone visit Period 2 week 12 and patient returns all study medication 2 before Period 2 week 12.

VISIT PERIOD 2 WEEK 12: (SITE VISIT; =/- 3 DAYS)

Examinations

Vital signs: blood pressure (mm Hg), heart rate (min-1), weight (kg), temperature Physical examination:

- Head (including ENT and eyes)

- Lymphatic system

- Endocrine system

- Lungs and respiratory tract

- Peripheral vascular system

- Cardiovascular system

Cardiovascular system

- Gastrointestinal tract, liver, spleen

- Urogenital system

- Nervous system

- Muscular and skeletal system

- Skin and connective tissue

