Review of glucose diary and			Χ	X	Х	Х	Х	X	Х	Х		
hypoglycemic protocol and												
reporting form												
Assessment of response ^h					Χ				Х			
PROMIS questionnaires, SF36,	Х			Х	Х	Х		Х	Х	Х		
PROBE												
Study drug dispensation		Χ			X ⁱ	Χ						
Study drug collection										X^{j}		

^a Clinical PDAI excluding pouchoscopy

^bCBC, AST, ALT, AP, Bilirubin, Creatinine, CRP. Serum samples for GLP-1 baseline fasting if possible (Screening or week 0).

^c Subject diary will be maintained electronically and completed daily reporting stool frequency, rectal bleeding, fecal urgency or abdominal cramps, and/or fever. The patient will complete this diary each day, beginning with the screening visit and ending at the visit. The average 7-day bowel frequency will be calculated for each 7-day period. For the clinical PDAI scores the last three days of diary entries before each visit will be used to calculate stool frequency and fecal urgency/abdominal pain scores.

^d Phone visit only with review of diaries and dose increase of study drug if tolerated. Patient will mail stool sample calprotectin or bring in person.

^f Crossover occurs after at least 5 days of washout after the last study dose

^g Pregnancy test at week 4 in case of early crossover

h Assessment of response: If average weekly bowel frequency of patient did not decrease by at least 15% compared to baseline the patient can proceed to early crossover (Period 1 week 4) or early termination (Period 2 week 10).

Non-responder at Period 1 week 4 receive study drug for period 2 to start 5 days after the last study dose of period 1

^jCollection of study drug from non-responders in Period 2 week4 and all patients who were responding at Period 2 week 10 and completed study at Period 2 week 12.

^k For non-responders at Period 2 week 10 the safety outcomes below will be assessed at Period 2 week 12. For this patient group at Period 2 week 12 only adverse events (review adverse events diary) and concomitant medication will be assessed at Period 2 week 12. An alternative approach is a phone visit at Period 2 week 12 (similar to the final visit at Period 2 week 14) and patient returns all study medication from period 1 and 2 before Period 2 week 12.

REFERENCES

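### Time on treatment depends on response at week 4, so an adverse event comparison over all exposure is modestly tilted; a common 4-week window and exposure-based rates would remove or show the tilt

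*Combined protocol and SAP*

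**What the plan says.** The second study aim is comparative: "To study safety, tolerability and quality of life in the trial period of liraglutide vs placebo". Each period is planned for 6 weeks, but its length can depend on response.

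- Study Design: "patients not responding to the respective therapies in period 1 may be crossed over after 4 weeks of therapy", and "in period 2 can be terminated early at week 4".
- Overview of Trial Sequence, visit week 4, gives the threshold: "at least a 15% decrease compared to baseline the patient can proceed to early crossover". Footnote h of the visit table says the same and extends it to early termination at week 10.
- Study Visits, period 2 week 10, is firmer: "If non-responder, patient should stop medication and will be considered early termination".
- Overview of Trial Sequence, visit week 10, instead classes non-response at that visit as the end of treatment.

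Under the study drug section, the highest dose level is planned from treatment week 3 to week 6.

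The safety analyses cover everyone with at least one dose. They list the "Number of study patients, who discontinued therapy", adverse events by body system and laboratory changes. Study Outcomes adds changes in nausea, appetite, abdominal pain and well-being. Neither section gives a time window for adverse events, a rate per unit of exposure, a rule assigning events to a treatment, or a definition of discontinuing therapy. By contrast, Study Outcomes sets the primary outcome at weeks 4 and 10, keeps the secondary bowel-frequency outcomes to weeks 1-4 and 7-10, and makes weeks 5-6 and 11-12 exploratory.

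**The concern.** The efficacy response decides how long a patient stays on each treatment, and adverse events accumulate with time on treatment. If liraglutide does what the study hypothesis expects, fewer patients leave it early, so liraglutide collects more patient-weeks than placebo. The extra weeks all fall in the top-dose stage. A table of events over all exposure would then show more events on liraglutide even if the weekly risk were identical.

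The discontinuation item raises a related question. Lack of efficacy is a listed reason for stopping study drug, and a week-10 non-responder is labelled early termination in one section. Without a definition, a reader of the results could not tell whether the count describes tolerability, efficacy or both.

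Future Perspective makes a larger trial conditional on this study raising no safety concerns. With 10 patients, these descriptive tables are the main safety evidence for that decision.

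**Working it through.** The plan gives no figure for exposure, response rate or uptake of early exit, so there is no stated value to reproduce. The check takes the time structure from the plan and treats response and uptake as assumptions.

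**Inputs from the documents.** Planned length is 6 weeks per period. The early exit point is treatment week 4, open only to patients with less than a 15% fall. The top dose level covers treatment weeks 3-6, which is 4 weeks. There are 10 patients, allocated 1:1 to the two sequences.

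**Assumptions.** p is the proportion with at least a 15% fall at treatment week 4. u is the share of non-responders who take the early exit. No one stops for another reason.

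**Mean weeks on a treatment** = 6 − 2u(1 − p).

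- p = 0.7 on liraglutide and 0.2 on placebo, u = 1: 6 − 2(0.3) = 5.4 and 6 − 2(0.8) = 4.4. Ratio 5.4/4.4 = 1.23.
- Same p, u = 0.5: 6 − 0.3 = 5.7 and 6 − 0.8 = 5.2. Ratio 5.7/5.2 = 1.10.

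Other assumed values:

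| p liraglutide / p placebo | ratio, u = 1 | ratio, u = 0.5 |
|---|---|---|
| 1.0 / 0 (extreme) | 6/4 = 1.50 | 6/5 = 1.20 |
| 0.8 / 0.2 | 5.6/4.4 = 1.27 | 5.8/5.2 = 1.12 |
| 0.6 / 0.3 | 5.2/4.6 = 1.13 | 5.6/5.3 = 1.06 |
| 0.5 / 0.5 | 1.00 | 1.00 |
| 0.3 / 0.6 | 4.6/5.2 = 0.88 | 5.3/5.6 = 0.95 |

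The ratio can run from 4/6 = 0.67 to 6/4 = 1.50.

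**Mean weeks at the top dose level** = 4 − 2u(1 − p). At 0.7 against 0.2 with u = 1 this is 3.4 against 2.4, ratio 1.42. The bound is 4/2 = 2.0.

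**What this does to a table.** Assume the same risk of 0.10 per week on both treatments, p = 0.7 against 0.2, and u = 1. The share of patients with at least one event is 1 − p(0.9⁶) − (1 − p)(0.9⁴).

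- Liraglutide: 1 − 0.7(0.531) − 0.3(0.656) = 0.431.
- Placebo: 1 − 0.2(0.531) − 0.8(0.656) = 0.369.

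In 10 patients that is about 4.3 against 3.7, a difference of 0.6 of a patient.

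**What is not affected.** Everyone still on treatment has the same planned 4 weeks before any exit for non-response, so events starting in treatment weeks 1-4 are compared over equal planned exposure, give or take the ±3-day visit window. Blood tests at weeks 4 and 10 also precede any such exit.

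**Discontinuation count**, same p, u = 1, before any stop for intolerance:

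- Exits for non-response not counted: 0 against 0.
- Period 2 early terminations counted, about 5 patients per treatment: 5 × 0.3 = 1.5 on liraglutide and 5 × 0.8 = 4 on placebo.
- Period 1 early crossovers counted as well: 10 × 0.3 = 3 and 10 × 0.8 = 8.

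The documents do not say which count is meant.

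**The case against.** Most of the opposing case bears on size, and much of it stands.

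- **Early exit is largely optional.** Study Design, the week-4 visit text and footnote h all use permissive wording; only the period 2 week-10 visit directs the patient to stop. Lower uptake shrinks the ratio, as the u = 0.5 column shows.
- **The response rates are assumed.** No section supplies them, and equal response gives no distortion.
- **The unit of the adverse event table is not stated.** Raw counts are one reading. The 23% excess in events also requires a constant weekly rate, although the dose rises over weeks 1-3 and events may cluster there.
- **The consequence is descriptive.** No safety test is planned, and a difference of this size is well within chance in 10 patients.

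A reader might infer that the plan's tolerability measures as a whole are driven by efficacy, with adverse events biased one way and discontinuations the other. The documents do not support that. Four safety and tolerability measures are listed, and the week-4 and week-10 laboratory values are taken before early exit can alter exposure. Nor is a discontinuation bias of 8 against 3 shown: no section calls a period 1 early crossover a discontinuation, those patients go on to period 2 treatment, and one section treats week-10 non-response as end of treatment. The withdrawal section requires a primary reason and lists withdrawals for adverse events apart from stops for lack of efficacy.

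None of this supplies a common window or an exposure denominator for adverse events.

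**Conclusion.** The concern holds in a limited form. Exposure can differ between treatments because of response, and the safety section neither restricts nor adjusts for it. If liraglutide works, an all-exposure adverse event comparison is tilted toward more events on liraglutide. The exposure ratio is at most 1.50. It is 1.23 with full uptake and 1.10 with half uptake under assumed response of 70% against 20%, and 1.00 if response is equal. Carrying the ratio over to event counts further assumes a roughly constant event rate.

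For discontinuations the finding is a missing definition, not a demonstrated bias. The secondary outcome can stay as it is if it is broken down by reason.

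Separately, the statements on whether a non-responder may or should leave treatment, and whether that exit is early termination or end of treatment, do not agree and must be reconciled. The size of the imbalance depends on how they are applied.

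**What to change.** Amend the safety analyses under Data Analysis as follows.

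1. Make the liraglutide-placebo comparison of adverse events the first 4 weeks of dosing in each period, by treatment at onset. This matches the window already used for the main efficacy outcomes.
2. Beside it, show all on-treatment adverse events with patient-weeks of exposure and rates per patient-week. List events that start during washout, or in the two weeks off drug after early termination, separately.
3. Keep the number who discontinued therapy, but tabulate it by treatment and by the primary reason already recorded. Show week-4 early crossover and week-10 early termination for non-response apart from stops for adverse events.
4. Reconcile the statements on early exit.

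The cost is mainly wording. Onset date and time and the primary reason for stopping are already documented, and visit timing gives the exposure. Routine recording of first and last dose dates is not stated outside serious adverse event reports, so the plan should name the source for patient-weeks.

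There are two small downsides. Events in weeks 5-6 and 11-12, half of the planned top-dose stage, appear only in the all-exposure table. Rates per patient-week assume a roughly constant event rate, and if events cluster during dose escalation, longer exposure dilutes the rate. That is a reason to show both tables.
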